### **1.5.2 Risk/Benefit for BMS-986148 and Nivolumab Combination Therapy**

Nivolumab has demonstrated clinical activity in subjects with advanced NSCLC, renal cell carcinoma, melanoma, and lymphomas, as well as other tumors, including ovarian, gastric, and mesothelioma. The clinical activity of nivolumab monotherapy observed to date in these malignancies suggests the potential for improved clinical outcomes relative to other approved therapies.

Nivolumab has demonstrated a manageable safety profile. The overall safety experience, when used either as a monotherapy or in combination with another therapeutic, is based on experience in approximately 8,600 subjects treated to date. There is no pattern in the incidence, severity, or causality of AEs with respect to nivolumab dose level. The most common AEs (as of 01 July

2016) include fatigue, rash, pruritus, diarrhea, and nausea. Side effects of nivolumab therapy may include those associated with immune-mediated activation, such as pneumonitis, thyroiditis, and hepatitis. Most of these events resolved with immune-modulating medication. To mitigate risk from serious immune-mediated AEs, subject management algorithms for nivolumab-related AEs from prior collective nivolumab experience have been included ([Appendix 3](#)).

There is potential for overlapping toxicity between clinical findings of BMS-986148 and nivolumab-related hepatotoxicity, infusion-related reactions, and peripheral neuropathy.

Elevation of the liver transaminases were the DLTs noted in 4 of the 10 subjects treated with BMS-986148 at 1.6 mg/kg Q3W. This dose is above the MTD, and no additional subjects will be treated at this dose. At the selected starting dose of BMS-986148 of 0.8 mg/kg IV Q3W, no DLTs were observed in the 4 evaluable subjects. However, the incidence of nivolumab-related hepatitis is quite low (approximately 1%). Subjects in this study receiving BMS-986148 monotherapy or BMS-986148 and nivolumab combination therapy will be monitored closely for any LFT abnormalities via laboratory assessments and frequent assessment for the development of symptoms. Study drug will be discontinued for any significant LFT abnormalities.

Peripheral neuropathy related to BMS-986148 is infrequent. No events related to study drug are noted to date as of 01 July 2016. Details of these events are summarized in [Section 1.5.1](#). For nivolumab monotherapy, the incidence of neuropathies was < 1%, and management guidelines have been established as detailed in the nivolumab IB. To minimize potential risks, criteria excluding subjects with peripheral neuropathy and dose modifications have been developed. In addition, subjects in this study receiving BMS-986148 monotherapy or BMS-986148 and nivolumab combination therapy will be monitored closely for any peripheral neuropathy via neurologic assessments and frequent assessment for the development of neurologic symptoms. Study drug will be discontinued for any significant neurologic developments.

Infusion reactions, including high-grade hypersensitivity reactions, following administration of nivolumab are uncommon. For BMS-986148, no infusion reactions have been reported to date (as of 01 July 2016 data cut-off date). Subjects will be monitored during the first cycle of the combination therapy and will continue to be monitored during subsequent cycles. Detailed management guidelines for infusion reactions are provided (see [Section 4.5](#)).

Significant ocular toxicities as seen in the preclinical toxicology studies have not been noted in the study thus far. For nivolumab monotherapy, the incidence of uveitis was < 1%, and management guidelines have been established as detailed in the nivolumab IB. Subjects will continue to be monitored by ophthalmologic examination for ocular symptoms, throughout the study treatment.

Subjects enrolling in Part 3 will have advanced solid tumor malignancies that has relapsed after standard of care chemotherapy or available therapies. The potential synergistic effects of nivolumab with BMS-986148 and the risk/benefit ratio support evaluation of this combination.

## **2 ETHICAL CONSIDERATIONS**

### **2.1 Good Clinical Practice**

This study will be conducted in accordance with Good Clinical Practice (GCP), as defined by the International Conference on Harmonisation (ICH) and in accordance with the ethical principles underlying European Union Directive 2001/20/EC and the United States Code of Federal Regulations, Title 21, Part 50 (21CFR50).

The study will be conducted in compliance with the protocol. The protocol and any amendments and the subject informed consent will receive Institutional Review Board/Independent Ethics Committee (IRB/IEC) approval/favorable opinion prior to initiation of the study.

All potential serious breaches must be reported to Bristol-Myers Squibb (BMS) immediately. A serious breach is a breach of the conditions and principles of GCP in connection with the study or the protocol, which is likely to affect, to a significant degree, the safety or physical or mental integrity of the subjects of the study or the scientific value of the study.

Personnel involved in conducting this study will be qualified by education, training, and experience to perform their respective tasks.

This study will not use the services of study personnel where sanctions have been invoked or where there has been scientific misconduct or fraud (eg, loss of medical licensure, debarment).

### **2.2 Institutional Review Board/Independent Ethics Committee**

Before study initiation, the investigator must have written and dated approval/favorable opinion from the IRB/IEC for the protocol, consent form, subject recruitment materials (eg, advertisements), and any other written information to be provided to subjects. The investigator or BMS should also provide the IRB/IEC with a copy of the IB or product labeling information to be provided to subjects and any updates.

The investigator or BMS should provide the IRB/IEC with reports, updates and other information (eg, expedited safety reports, amendments, and administrative letters) according to regulatory requirements or institution procedures.

### **2.3 Informed Consent**

Investigators must ensure that subjects are clearly and fully informed about the purpose, potential risks, and other critical issues regarding clinical studies in which they volunteer to participate.

In situations where consent cannot be given to subjects, their legally acceptable representatives (as per country guidelines) are clearly and fully informed about the purpose, potential risks, and other critical issues regarding clinical studies in which the subject volunteers to participate.

BMS will provide the investigator with an appropriate (ie, Global or Local) sample informed consent form(s) which will include all elements required by ICH, GCP, and applicable regulatory requirements. The sample informed consent form will adhere to the ethical principles that have their origin in the Declaration of Helsinki.

Investigators must:

- Provide a copy of the consent form(s) and written information about the study in the language in which the subject is most proficient prior to clinical study participation. The language must be nontechnical and easily understood.
- Allow time necessary for subject or subject's legally acceptable representative to inquire about the details of the study.
- Obtain an informed consent signed and personally dated by the subject or the subject's legally acceptable representative and by the person who conducted the informed consent discussion.
- Obtain the IRB/IEC's written approval/favorable opinion of the written informed consent form(s) and any other information to be provided to the subjects, prior to the beginning of the study, and after any revisions are completed for new information.
- If informed consent is initially given by a subject's legally acceptable representative or legal guardian, and the subject subsequently becomes capable of making and communicating his or her informed consent during the study, consent must additionally be obtained from the subject.
- Revise the informed consent whenever important new information becomes available that is relevant to the subject's consent. The investigator, or a person designated by the investigator, should fully inform the subject or the subject's legally acceptable representative or legal guardian, of all pertinent aspects of the study and of any new information relevant to the subject's willingness to continue participation in the study. This communication should be documented.

The confidentiality of records that could identify subjects must be protected, respecting the privacy and confidentiality rules applicable to regulatory requirements, the subjects' signed informed consent form and, in the US, the subjects' signed Health Insurance Portability and Accountability Act Authorization.

The consent form(s) must also include a statement that BMS and regulatory authorities have direct access to subject records.

The rights, safety, and well-being of the study subjects are the most important considerations and should prevail over interests of science and society.

### **3 INVESTIGATIONAL PLAN**

[figure not shown]
#### **3.1 Study Design and Duration**

This is a Phase 1/2a, open-label study to characterize the safety and tolerability, as well as preliminary efficacy, PK, and PD of BMS-986148 administered alone and in combination with nivolumab in subjects with select advanced solid tumors (pancreatic, ovarian, NSCLC, gastric, or mesothelioma). The study has 3 segments: Part 1 (Phase 1 study - dose escalation), Part 2 (Phase 2a - dose expansion), and Part 3 (BMS-986148 in combination with nivolumab; Part 3A - dose escalation and Part 3B - dose expansion) (see [Figure 3.1-1](#)). All subjects will complete up to 4 study periods: Screening (up to 28 days), Treatment (21 days/cycle Q3W or 28 days/cycle QW), Follow-up (60 or 100 days), and Survival Follow-up (see [Figure 3.1-2](#)). After completing the Follow-up period, subjects will continue to be followed for [REDACTED] up to 2 years from first dose

of study drug for subjects discontinuing study drug prior to 2 years. Subjects receiving study drug for more than 2 years will be followed in the Survival Follow-up period for 6 months from their last treatment date. With Amendment 3, a dose escalation phase will be conducted with BMS-986148 and nivolumab combination therapy (Part 3A). In the BMS-986148 and nivolumab combination therapy dose expansion phase (Part 3B), additional subjects with pancreatic, ovarian, NSCLC, gastric, or mesothelioma will be treated at or below the MTD of the combination dose identified in Part 3A to confirm safety and evaluate anti-tumor activity.

[figure not shown]
The duration of the study is anticipated to be approximately 5 years from the time of the first visit of the first subject to the required Survival Follow-up of the last subject enrolled. The end of the study will occur when the last subject has the last Survival Follow-up visit.

**Figure 3.1-1: Sequence of Study Phases**

QW: every week; Q3W: every 3 weeks.

**Figure 3.1-2: Dosing (Q3W and QW) and Study Periods**

Note: Subjects treated for > 2 years will be followed for 6 months after EOT in the Survival Follow-Up. Additionally, specifically in Part 3, treatment duration is 24 weeks to a maximum of 48 weeks.

C1D1: Cycle 1 Day 1 (first dose); D: day; DLT: dose-limiting toxicity; EOT: end of treatment; QW: every week; Q3W: every 3 weeks.

### **3.1.1 Dose Escalation (Part 1)**

Part 1 is divided into 2 sections. In Part 1A, BMS-986148 will be administered with Q3W dosing (21 days/cycle), and in Part 1B, BMS-986148 will be administered with QW dosing for 3 weeks followed by 1 week off (28 days/cycle). Part 1B may be initiated once the MTD or a tolerated dose below the MTD for Part 1A is established.

#### **Part 1A: BMS-986148 Administered Every 3 Weeks**

Approximately 30 subjects will be enrolled in ascending dose cohorts starting with a dose of 0.1 mg/kg. BMS-986148 will be administered Q3W in a 21-day cycle. The approach for selection of the next dose at each escalation step and the rules for escalation decision based on DLT criteria guided by the mTPI design are described below, with more details in [Section 4.5.1](#).

#### **Part 1A: Selection of Doses**

A modified Fibonacci dose escalation will be used.

The first cohort of subjects will receive a starting dose of 0.1 mg/kg. Dose escalation for each subsequent cohort of subjects will be guided by the incidence of BMS-986148-related AEs as graded by NCI Common Terminology Criteria for Adverse Events version 4.03 (NCI CTCAE v4.03) in the first 3 weeks of dosing (DLT evaluation period). Dose escalation will be in increments of 100% above the previous dose level until the first occurrence of any of the following: DLT,  $\geq$  Grade 3 decrease in neutrophil count lasting > 72 hours,  $\geq$  Grade 3 thrombocytopenia lasting > 72 hours,  $\geq$  Grade 2 ocular toxicity, or 2 subjects with  $\geq$  Grade 2 AEs in a single dose level cohort and considered related to BMS-986148 with the following exceptions: asymptomatic electrolyte abnormalities that can be managed with appropriate supplements and Grade 2 alopecia. In addition, Grade 2 fatigue that is less than 2 grades from baseline (ie, from Grade 1 to Grade 2) will not trigger a Fibonacci sequence. Once one or more of the above occur, a modified Fibonacci dose escalation will be employed for any subsequent dose escalations, with increments of 67%, 50%, 40%, and 33%. Any further dose escalations will be 33%.

Intermediate doses may be evaluated if agreed upon by the BMS Medical Monitor and investigators. The next dose level will not exceed 100% or the dose increment per the modified Fibonacci dose escalation.

#### **Part 1A: Dose Escalation Decision Rules**

Enrollment in dose escalation and selection of the MTD will adhere to a mTPI design. The design provides a simple algorithm to guide decisions on escalation, expanding at the same dose, and de-escalation, depending on the number of observed toxicities after each dose cohort (see [Figure 3.1.1-1](#)). The mTPI method utilizes a target toxicity (DLT) rate and equivalence interval

(EI) to guide decisions on escalation after each cohort and to estimate the MTD. For this study the target DLT rate is 27%, and the EI is 25% to 29%.

Dose escalation will begin at a dose of 0.1 mg/kg dose (Dose Level 1) and will be guided by the cumulative number of subjects who are DLT evaluable and who experience a DLT. An initial cohort of 2 subjects will be enrolled to Dose Level 1 and subsequently dose level 2 (if no DLTs in Dose Level 1 and criteria above for transitioning from 100% increment to Fibonacci is not met) in Part 1A; otherwise, 3 to 4 patients will be treated. In the first cohort, a 5-day interval is required between Cycle 1, Day 1 dosing for the first 2 subjects (ie, 5 days between Cycle 1, Day 1 dosing for subjects 1 and 2). An initial cohort of 3 subjects will be enrolled to all other dose levels in Part 1A. A fourth subject may be enrolled in a dose escalation cohort following agreement between the investigator and the BMS Medical Monitor if able to start the first day of dosing within approximately 1 week of the third subject in the same dose escalation cohort. At any dose level, if the suggested decision by the mTPI design is to expand the same dose, 3 more subjects will be enrolled. If the suggested decision is to treat more subjects at a given dose level as specified by the mTPI algorithm when there are already at least 13 DLT evaluable subjects treated at the same dose level or a total of 30 DLT evaluable subjects treated, the dose escalation phase will be stopped.

Decisions to escalate, add more subjects to the current dose, de-escalate, or de-escalate and declare the current dose as unacceptable (exceeding the MTD), will be based on the rate of DLTs in evaluable subjects within the 21-day DLT evaluation period for Part 1A guided by the mTPI model and posterior inference (Figure 3.1.1-1 and Appendix 1). At least 2 DLT-evaluable subjects treated at each of the lowest 2 dose levels and at least 3 DLT-evaluated subjects treated at each of the other dose levels are required to enable decision making. Subjects with insufficient data to establish safety during the DLT evaluation period at the dose tested (eg, omitted or reduced doses for reasons other than a DLT) may be replaced upon agreement of the BMS Medical Monitor and investigators.

[figure not shown]
In addition, if dose modifications for ocular toxicity occur in 2 or more subjects within the first 5 subjects treated on study, or if with greater patient numbers > 20% of subjects require a dose modification due to ocular toxicity, enrollment will be suspended at all dose levels equal to or greater than the lowest dose level with a dose modification due to ocular toxicity, in order to assess the safety data. Enrollment may continue at lower dose levels where no dose modifications have occurred due to ocular toxicity while this safety assessment is being conducted.

There will be no intrasubject dose escalation of BMS-986148.

Figure 3.1.1-1 shows examples of scenarios guiding decision making that may be encountered during dose escalation with respect to the number of DLT evaluable subjects and the number of subjects with a DLT. All potential combinations of the number of DLTs and number of treated subjects evaluable for DLT are shown in Appendix 1. In addition to escalation or expansion decisions, dose re-escalation is permitted as per Figure 3.1.1-1 and Appendix 1 after a decision to de-escalate is made, except when a dose has been identified as exceeding the MTD. Therefore, a dose level could be revisited multiple times under the mTPI design.

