### **Part 1B: BMS-986148 Administered QW for 3 Weeks and 1 Week Off**

Approximately 24 subjects will be enrolled in ascending dose cohorts. Part 1B may begin after determining the MTD or a tolerated dose below the MTD in Part 1A. The starting dose for Part 1B will be chosen by modeling active ADC concentration-time data from Part 1A and selecting a fractionated dose that provides similar exposure to that of the MTD or a tolerated dose below the MTD. In the event that concentration-time data are not available for modeling, the starting dose will be 1/3rd of the MTD or a tolerated dose below the MTD from Part 1A. In Part 1B, BMS-986148 is administered every week for 3 weeks and 1 week off in a 28 day cycle.

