### **Part 1B: Dose Escalation Decision Rules**

The same mTPI design (Figure 3.1.1-1 and Appendix 1) as in Part 1A will be used to help guide escalation decisions except that all dose levels in Part 1B begin with an initial number of 3 to 4 subjects. A fourth subject may be enrolled in a dose escalation cohort following agreement between the investigator and the BMS Medical Monitor if able to start the first day of dosing within approximately 1 week of the third subject in the same dose escalation cohort. The DLT evaluation period will be 28 days. At least 3 DLT-evaluable subjects treated at each of the dose levels in Part 1B will be required to enable a decision to escalate, add more subjects to the current dose level, or de-escalate. Subjects must receive 3 doses in Part 1B during the DLT evaluation period (unless DLT has occurred) to be considered evaluable for dose escalation decisions. Subjects with insufficient data to establish safety during the DLT evaluation period at the dose tested (eg, omitted or reduced doses for reasons other than a DLT) may be replaced upon agreement of the BMS Medical Monitor and investigators.

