#### **3.1.2 Dose Expansion (Part 2)**

The purpose of the cohort expansion will be to assess preliminary antitumor efficacy, expanded safety experience, and PD effects of BMS-986148. Additional subjects will be treated after the completion of Part 1A and/ or Part 1B, at the MTD, or at an alternative dose below MTD as agreed upon by the BMS Medical Monitor and investigators. Part 2 can begin before the completion of Part 1B as the Q3W dosing regimen is the intended regimen for Part 2. However, if the aggregate PK and safety data indicate similar safety but higher cumulative exposure with the QW dose schedule, this schedule may also be evaluated in Part 2 in an additional cohort of 25 to 26 subjects, once the MTD or a tolerated dose below the MTD is identified in Part 1B. Treatment doses in the cohort expansion groups will not exceed the MTD.

Five expansion cohorts will be restricted to these tumor types 1) mesothelioma 2) pancreatic 3) ovarian 4) NSCLC, and 5) gastric cancer. Enrollment in cohort expansion will be determined by the mesothelin expression of the archived tumor sample (or fresh tumor sample if archived sample is not available).

The enrollment in each expansion cohort will be guided by a Simon 2-Stage design framework (see [Table 8.1-1](#)) exploring efficacy in the following 2 populations: [REDACTED]

Anti-tumor activity will be assessed initially in approximately 12 to 15 evaluable subjects per tumor type (Stage 1) treated in each monotherapy cohort, with the option to stop enrolling in a cohort without an initial anti-tumor activity signal. The number of subjects needed for the Stage 1 review is guided by a Simon 2-Stage design as shown in Table 8.1-1 below for each tumor type with futility boundaries as follows: after Stage 1, if none of the first 15 evaluable subjects in the gastric or pancreatic cohorts, if  $\leq 2$  of the first 12 with mesothelioma, or  $\leq 1$  of the first 14 with NSCLC or ovarian cohort demonstrate clinical activity, enrollment in the cohort meeting criteria may be stopped for this population.

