Clinical Drug Supplies									
Dose Level Assignment		X							At the completion of screening procedures and eligibility determination.
BMS-986148 Administration			X			X	X		Those supplied by BMS.

a In the event multiple procedures are required at a single time point, the following is a list of procedures from highest priority to low: 1) ECG, 2) PK sampling, and 3) clinical labs.

b C1D4: ± 1 day.

c Ophthalmological examination: 8-point exam (visual acuity, pupils, extraocular motility and alignment, tonometry, visual field, external examination, slit lamp examination and fundoscopy) conducted at baseline and focused exams with visual acuity, slit lamp, and as indicated will be conducted at the end of Cycle 1 (pre-dose Cycle 2), every other cycle, EOT and as clinically indicated during the study.

d Cycle 1, Day 1: vital signs will be obtained before the BMS-986148 infusion and then every 15 minutes (± 5 minutes) until 60 minutes after completion of the infusion. During subsequent treatment visits, vital signs may be obtained every 30 minutes (± 10 minutes) until 30 minutes following completion of the last infusion. If any vital sign is abnormal at the final check, the subject must be observed further for a period of time, as clinically indicated. The start and stop time of the study drug infusion should be documented (start of drug infusion = 0 hour).

█ C: cycle; CBC: complete blood cell (count); CRF: case report form; D: day; █  
█ ECG: electrocardiogram; ECOG: Eastern Cooperative Oncology Group; EOI: end of infusion; EOT: end of treatment; IHC: immunohistochemistry; LVEF: left ventricular ejection fraction; MUGA: multigated acquisition; PE: physical examination; PK: pharmacokinetics; QTcF: QT interval corrected by Fridericia's formula; SAE: serious adverse event.

**Table 5.1-5: Cycle 2 to Off Study Visit, Part 1B (Weekly Dosing BMS-986148 Monotherapy Dosing / 28 Day Cycle) Procedural Outline (CA008002)**

Procedure a	C2 and C3				C4				C5 and Beyond			EOT	Follow-up (30 and 60 Days After Last Dose)	Survival Follow- up b	Notes	
	D1	D8	D15	D22	D1	D2	D4 c	D8	D15	D1	D8	D15		(±5 days)		(±2 weeks)
Safety Assessments																
Targeted PE	X	X	X	X	X						X			X	X	To include signs and symptoms of peripheral neuropathy and ocular toxicity. Any grade ocular toxicity requires ophthalmologist consultation and discussion with medical monitor as appropriate.

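### The ocular enrollment pause is stated only under Part 1A, without a clear denominator, and may give little or no protection on the weekly schedule in Part 1B

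*Protocol*

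**What the plan says.** The rule appears once, in Protocol Section 3.1.1, Part 1A: Dose Escalation Decision Rules. It is triggered by 2 or more ocular dose modifications in the "first 5 subjects treated on study, or if with greater patient numbers > 20% of subjects require a dose modification due to ocular toxicity". When it is triggered, "enrollment will be suspended at all dose levels equal to or greater than the lowest dose level with a dose modification due to ocular toxicity", so that the safety data can be assessed. Lower levels with no ocular modification may continue to enroll.

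The Part 1B decision rules say: "The same mTPI design (Figure 3.1.1-1 and Appendix 1) as in Part 1A will be used to help guide escalation decisions". They change the cohort size ("all dose levels in Part 1B begin with an initial number of 3 to 4 subjects"), lengthen the DLT window to 28 days and add an evaluability condition: "Subjects must receive 3 doses in Part 1B during the DLT evaluation period (unless DLT has occurred) to be considered evaluable". They do not mention the ocular rule. On size, the Part 1B text says: "Approximately 24 subjects will be enrolled in ascending dose cohorts".

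Two other sections bear on the count. Section 1.5.1 reports no significant eye toxicity in the 30 subjects dosed in Part 1A by 1 July 2016, but not how many had an ocular dose modification. Section 3.1.2 says: "Part 2 can begin before the completion of Part 1B as the Q3W dosing regimen is the intended regimen for Part 2". Further Q3W subjects may therefore be on study while Part 1B is enrolling.

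**The concern.** Part 1B is a new weekly schedule. The sponsor judged a numeric ocular pause necessary for Part 1A, and nothing in the protocol explains leaving it out or diluting it in Part 1B.

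The mTPI algorithm need not fill the gap. Table 4.5.2-1 requires interruption and a one-level decrease for Grade 2 uveitis, eye pain or loss of acuity that improves on topical therapy. Under Section 4.5.1 the same event is not a DLT unless it needs systemic treatment or fails topical therapy. If it costs a weekly dose in Cycle 1, the subject is no longer evaluable and may be replaced, so mTPI does not count it then either. If it is confirmed as topical-responsive after all three doses, the subject counts as evaluable without a DLT.

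Three such subjects out of three enter Appendix 1 as 0/3 DLTs, which reads escalate. The step is at most 67%, because a Grade 2 ocular event ends the 100% increments. Whether enrollment stops for review would then depend on judgment, not on a stated limit.

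**Working it through.** The protocol gives no operating characteristics for the ocular rule, so there is no plan figure to reproduce.

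**Inputs.** From the protocol: 30 Q3W subjects (Section 1.5.1); weekly levels of 3 or 4 subjects, with 3 more if mTPI says stay; about 24 subjects in Part 1B; thresholds of 2 in the first 5 and then > 20%. Assumed: *e* = 0 or 1 earlier ocular modifications.

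**Pooled count.** The first limb cannot fire, because the first 5 subjects on study were treated in Part 1A. The second fires if (*e* + *x*)/(30 + *n*) > 0.20, with *x* of *n* weekly subjects affected.

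| Weekly level | *e* = 0 | *e* = 1 | *e* = 2 |
|---|---|---|---|
| 3 of 3 | 3/33 = 9.1% | 4/33 = 12.1% | 5/33 = 15.2% |
| 6 of 6 | 6/36 = 16.7% | 7/36 = 19.4% | 8/36 = 22.2% (fires) |

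The 3-of-3 result is robust: even *e* = 3 gives 6/33 = 18.2%. The 6-of-6 result is tighter. With *e* = 1 and 29 earlier subjects, 7/35 = 20.0% does not exceed the limit, but with 28 earlier subjects 7/34 = 20.6% does. Unaffected subjects at earlier weekly levels dilute the count further: 3 more give 7/39 = 17.9%.

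Over all 24 weekly subjects the pooled rule can fire, but late. It needs 11 affected with *e* = 0 (11/54 = 20.4%) or 10 with *e* = 1. At a true rate of 40%, the binomial chance of that many by subject 24 is 0.35 or 0.51.

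**Rule confined to Part 1A.** There is then no count in Part 1B to compute.

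**Count restarted for Part 1B, same thresholds, checked after each subject.** The number of affected subjects that triggers a pause is 2 up to *n* = 9 (2/9 = 22.2%), 3 for *n* = 10 to 14, 4 for 15 to 19 and 5 for 20 to 24. For the first *n* = 3, 4 or 6 subjects the chance is 1 − (1 − *p*)^*n* − *np*(1 − *p*)^(*n* − 1). At *p* = 0.40 and *n* = 3 this is 1 − 0.216 − 0.432 = 0.352. For 24 subjects, enumerating paths to these limits gives the last column.

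| True rate | First 3 | First 4 | First 6 | All 24 |
|---|---|---|---|---|
| 5% | 0.7% | 1.4% | 3.3% | 8% |
| 10% | 2.8% | 5.2% | 11% | 28% |
| 40% | 35% | 52% | 77% | 99% |

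The pooled rule with *e* = 0 or 1 has a 0% chance of firing within the first 6 weekly subjects at any true rate.

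**How far mTPI overlaps.** Suppose 40% of weekly subjects need an ocular modification and a quarter of those events are DLTs, so the DLT rate is 10% (other DLTs ignored). After 3 subjects mTPI says escalate with probability 0.9³ = 0.73 and de-escalate (2 or more DLTs) with probability 0.028. It says stay after 1 of 3, with probability 0.243. Three more subjects then bring de-escalation with probability 0.028, so the cumulative chance is 0.028 + 0.243 × 0.028 = 3.5%. If half the events are DLTs (rate 20%), the figures are 0.8³ = 0.51 for escalate and 0.104 + 0.384 × 0.104 = 14.4% for de-escalate.

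**The case against.** The strongest objection is to the reading. The words on study qualify only the first limb, and the > 20% limb names no denominator. The action is ordered by dose level, which fits poorly with pooling Q3W and weekly levels. Section 5.3 points back to Section 3.1.1 from text about reducing or stopping the dose in one subject, so it does not settle whether the enrollment rule extends to Part 1B. This stands: a reader might infer that the rule certainly fails to fire in Part 1B, and the text does not support that much. But of the possible readings, only a restarted count protects Part 1B, and the text nowhere states one.

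Six of six is not the natural scenario. Non-DLT events alone lead mTPI to escalate at 0/3, so six subjects are reached only after a stay or through optional additions. This also stands, and 3 of 3 is the case to weigh.

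Other safeguards are real. Table 5.1-4 schedules targeted examinations on Days 8, 15 and 22 that cover ocular signs and symptoms, and requires ophthalmology consultation for ocular toxicity of any grade. Abnormal eye examinations must be discussed with the medical monitor before dosing. Dose steps shrink after a Grade 2 ocular event, and safety review is ongoing. An event first seen at the end-of-Cycle-1 examination may need up to two weeks of topical therapy before it can be classed as a non-DLT, so escalation should not be immediate. It would be wrong to infer that eye toxicity in Part 1B goes unmonitored. None of these checks, however, sets a number at which enrollment pauses.

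Finally, no significant eye toxicity was seen in 30 subjects, some of them at 1.6 mg/kg, and the weekly starting dose is meant to match a tolerated Q3W exposure. That lowers the weight but does not close the gap.

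**Conclusion.** The concern holds as a gap in a stated safety rule, of minor to moderate weight. On a pooled reading the early limb is spent and the 20% limb is too diluted to respond to a fully affected weekly level of 3. On a Part 1A-only reading there is no numeric ocular pause in Part 1B.

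The pooled figures assume about 30 earlier Q3W subjects and at most one earlier ocular modification. With two, six of six would fire, while three of three still would not. The 40% rate is a stress case. The documents report no ocular data on the weekly schedule, so nothing here implies that such a rate is expected. Section 1.5.1 describes nonclinical toxicities as dose dependent, but that remark directly follows the sentence on gut, liver and marrow, and this finding does not rely on it for the eye. Parts 2 and 3 are outside the finding; they have per-arm pauses at 29% and 31% for drug-related AEs requiring dose modification.

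**What to change.** Add to the Part 1B decision rules:

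> The ocular suspension rule of Part 1A applies in Part 1B, with the count restarted for weekly-schedule subjects. If 2 or more of the first 5 subjects treated in Part 1B, or more than 20% of Part 1B subjects thereafter, need a dose modification for ocular toxicity, Part 1B enrollment pauses at the lowest affected weekly level and at every weekly level above it.

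This keeps the thresholds and the review, uses data already collected, and makes clear that a weekly trigger does not by itself stop Q3W enrollment. One event in the first 3 to 5 subjects does not fire.

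Count over Part 1B, not per dose level. A per-level count would never fire if 1 of 3 were affected at each of eight levels (8/24 = 33%), whereas the Part 1B count fires by the sixth subject (2/6 = 33%). A per-level count may be added but should not replace it.

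The cost is one sentence in an amendment and some needless pauses: about 8% over 24 subjects at a true rate of 5%, and 28% at 10%. Each pause means a safety review, and lower unaffected levels may keep enrolling.
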